## 11.2 Demographics and Baseline Characteristics

The following demographic variables collected at screening will be summarized by treatment group: race, gender, age, height and weight.

## 11.3 Measurements of Treatment Compliance

Compliance to the study treatment was assessed through the patient diary and checked versus the used and unused study product containers given back by the patients.

Treatment compliance will be estimated as the ratio between the number of the administered doses and the number of planned doses.

Vers. No. 03, 05/02/18 (Ref. SOP No. 16)

# STATISTICAL ANALYSIS PLAN

Statistical Analysis Plan Version no. 1.0 – 20/07/2020

Protocol Code NORFLO-ORO-16 EudraCT number NA

## 11.4 Efficacy Analysis

## 11.4.1 Primary Efficacy Endpoints

The number and intensity of relapses were assessed through instrumental analysis and physical examination. These endpoints will be assessed from baseline to end of treatment.

When a relapse occurs, the data reported in the first unscheduled visit concerning the intensity of the relapse and data from LFM will be used as they are taken before the administration of both systemic and topical cortisone.

Mean and standard deviation will be used to describe the number of relapses per patient. The mean number of relapses per patient will be compared between the treatment groups using Student's t-test. ANOVA will be used to include predictive/confounding variables in the model.

In addition, a generalized linear mixed model (GLMM) with Poisson statistical distribution and with the number of relapses as dependent variable will be used to assess the effects of the treatment on reducing the number of relapses, also including in the model other potentially predicting/confounding variables.

The intensity of each relapse will be scored as mild (either trace to 1+ cell OR flare  $\leq 20$ ), moderate (2+ to 3+ cell OR Flare  $\geq 20$  and  $\leq 100$ ) and severe (4+ cell OR Hypopyon OR flare  $\geq 100$ ). For each patient, the average intensity will be estimated as the mean of the intensity of relapses observed during the study. The average and the maximum intensity will be compared between treatment groups using Student's t-test. ANOVA will be used to include predictive/confounding variables in the model. As this variable could likely be not normally distributed, Wilcoxon Mann-Whitney will be also used.

The mean number of relapses per patient observed during the study will be compared to the mean number of relapses reported the previous year within each treatment group using paired t-test. The patients will be classified based on the number of relapses before treatment, using the median number per subjects as a cut-off to separate subjects with a high number of relapses form those with a low number of relapses. The subjects will be classified on the number of relapses after treatment using the same cut-off. The patients that before and after treatment will change from the high number of relapses category to the low number category, will be considered as responders, while the others will be considered as non-responders. The proportion of responders will be compared between treatment groups using chi-square test.

The primary efficacy endpoints will be analyzed in the following hierarchical order: first, "the mean number and intensity of relapses during the study between treatment groups" and then "the reduction of mean number of relapses between the year before treatment and the study period".

The level of cell damage and inflammation will be assessed through Laser Flare Meter. The difference between treatment groups will be compared using ANCOVA, with the baseline level included in the model.

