5 CRITERIA FOR EVALUATION

5.1 **Primary Efficacy Endpoint**

The primary efficacy endpoint will be the mean number and intensity of relapses per patient occurred during the study, from baseline to end of treatment, in patients treated with the NORFLO[®] ORO compared to patients treated with placebo.

The reduction in relapses will be determined by a reduction of the intraocular inflammation through a clinical and diagnostic evaluation that includes Laser measurement of AC flare

with Kowa LFM 600 or LFM 700 (Normal range 2.5-7 ph/ms. Outside normal range > 10 ph/ms).

The reduction of the mean number of relapses per patient between the year before treatment and the study period within each treatment group will also be assessed.

The reduction of cell damage and inflammation will be measured by the Laser Flare Meter, in patients affected by HLA-B27-associated uveitis after treatment with NORFLO[®] ORO, when compared to placebo.

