8.4.1 Dosage/Dosage Regimen

Study products will be administered as follows.

Two single foil pouches per day, each with main meals, with an estimated interval of about 8 hours between doses. A minimum interval of 4 hours between doses should be maintained.

The treatment will last for a period of 12 months.

Table 3 - Dosage	Regimen
------------------	---------

	Dosage regimen/ Each center	Administration	Minimum interval between doses	Duration
NORFLO [®] ORO	3.49 gr (2 single foil pouches of 1.7450 g) per day	Each single pouch (1.7450 g) at main meal in a glass of water	4 hr	12 months
PLACEBO	3.49 gr (2 single foil pouches of 1.7450 g) per day	Each single pouch (1.7450 g) at main meal in a glass of water	4 hr	12 months

8.4.2 **Dispensing**

Investigator (or designee) delivers the study product to the patient at each visit.

8.5 **Supply of Study Product at the Site**

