10.4 Additional Unscheduled Visits in Case of Relapse

Should a relapse occur, an unscheduled visit will be performed including a complete ophthalmic evaluation. The number of cells in the AC will be determined by slit lamp, too.

Topical or systemic treatment will be prescribed to the subject according to the severity of the relapse and according to the best medical judgement.

Two following visits will be scheduled 2 and 6 weeks thereafter. During these visits a complete ophthalmic evaluation will be done.

If the subject is prescribed a systemic treatment for the relapse, he/she will be withdrawn from the study, and treated according to the best medical judgement.

If only topical treatments are prescribed, the subject will be allowed to continue the study. Depending on the onset time of the relapse it could be necessary to delay Visit 2 or Visit 3 around 2 months after the topical treatment conclusion.

Should Visit 2 be delayed, the delay will be recovered by keeping the date of Visit 3 at 12 months.

Should Visit 3 be delayed, the delay will not be recovered.

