11 DISCONTINUATION AND REPLACEMENT OF SUBJECTS

11.1 Early Discontinuation of Study Drug

A subject may be discontinued from the study treatment at any time if either the subject, and/or the investigator, and/or Eye Pharma feels that it is not in the subject's best interest to continue the study treatment. The following is a list of possible reasons for study treatment discontinuation:

- Subject withdrawal of consent
- Subject is not compliant with study procedures
- Need for the subject to start a systemic anti-inflammatory, immunosuppressive, biologicals therapy for uveitis or for other pathologies
- Adverse event that indicated in the opinion of the investigator that it would be in the best interest of the subject to discontinue study treatment
- Pregnancy
- Protocol violation requiring discontinuation of study treatment
- Missed follow-up
- Eye Pharma requests early study termination

If a subject is withdrawn from treatment due to an adverse event, the subject will be followed and treated by the investigator until the abnormal parameter or symptom has resolved or stabilized.

All subjects who discontinue the study treatment should come in for an early discontinuation visit as soon as possible and then they should be encouraged to complete all remaining scheduled visits and procedures.

All subjects are free to withdraw from participation at any time, for any reason, specified or unspecified, and without prejudice.

Reasonable attempts will be made by the investigator to obtain a reason for subject's withdrawals. The reason for the subject's withdrawal from the study will be specified in the subject's source documents.

11.2 **Replacement of Subjects**

Only subjects dropping out the study because they are beginning systemic therapy with antiinflammatory, immunosuppressive, biologic drugs will be replaced.

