### 5. STUDY ENDPOINTS

### 5.1 Primary Endpoints

The primary efficacy endpoint is the mean number and intensity of relapses per patient occurred during the study, from baseline to end of treatment, in patients treated with the NORFLO® ORO compared to patients treated with placebo.

The reduction in relapses was determined by a reduction of the intraocular inflammation through a clinical and diagnostic evaluation that includes Laser measurement of AC flare with Kowa LFM 600 or LFM 700 (Normal range 2.5-7 ph/ms, Outside normal range > 10 ph/ms).

The reduction of the mean number of relapses per patient between the year before treatment and the study period within each treatment group will also be assessed.

The reduction of cell damage and inflammation were measured by the Laser Flare Meter, in patients affected by HLA-B27-associated uveitis after treatment with NORFLO® ORO, when compared to placebo.

The number and intensity of relapses and LFM data, used in primary efficacy endpoints, were reported in the first unscheduled visit.

Only patients with relapses will be analyzed in primary efficacy endpoints.

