# 9.1.4 Methods for Withdrawals and Missing Data

A subject could be discontinued from the study treatment at any time if either the subject, and/or the investigator, and/or Eye Pharma feel that it is not in the subject's best interest to continue the study treatment. The following is a list of possible reasons for study treatment discontinuation:

- Subject withdrawal of consent
- Subject is not compliant with study procedures

Statistical Analysis Plan Version no. 1.0 - 20/07/2020

Protocol Code NORFLO-ORO-16 EudraCT number NA

- Need for the subject to start a systemic anti-inflammatory, immunosuppressive, biologicals therapy for uveitis or for other pathologies
- Adverse event that indicated in the opinion of the investigator that it would be in the best interest of the subject to discontinue study treatment
- Pregnancy
- Protocol violation requiring discontinuation of study treatment
- Missed follow-up
- Eye Pharma requests early study termination.

All subjects who discontinued the study treatment should come back for an early discontinuation visit as soon as possible and then they should be encouraged to complete all remaining scheduled visits and procedures.

All subjects were free to withdraw from participation at any time, for any reason, specified or unspecified, and

Reasonable attempts were made by the investigator to obtain a reason for subject's withdrawals. The reason for the subject's withdrawal from the study was specified in the subject's source documents.

No missing data will be replaced.

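### The window for the primary relapse count ends at an undefined end of treatment, and no rule covers relapses after a patient stops the product but stays in follow-up

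*SAP*

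**What the plan says.** The window appears in four places: Protocol 5.1 and 14.3, and SAP 5.1 and 11.4.1. SAP 11.4.1 states: "These endpoints will be assessed from baseline to end of treatment". The endpoint definitions combine two descriptions. Protocol 5.1 refers to "relapses per patient occurred during the study, from baseline to end of treatment", and SAP 5.1 to relapses that "occurred during the study, from baseline to end of treatment". The testing hierarchy in SAP 11.4.1 names only the study: "the mean number and intensity of relapses during the study between treatment groups".

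Neither document defines end of treatment. Protocol 8.4.1 gives the planned length: "The treatment will last for a period of 12 months". Planned participation is also about 12 months.

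Stopping the product is not the same as leaving the study. Protocol 11.1 asks product stoppers to attend an early discontinuation visit, and "then they should be encouraged to complete all remaining scheduled visits and procedures". SAP 9.1.4 repeats this: "they should be encouraged to complete all remaining scheduled visits and procedures". Some patients do leave. Protocol 10.4 says: "If the subject is prescribed a systemic treatment for the relapse, he/she will be withdrawn from the study". Protocol 8.2 withdraws patients after emergency unblinding.

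SAP 8.1 calls the efficacy set intention-to-treat. SAP 9.1.4 replaces no missing data. SAP 11.4.1 compares raw counts by t-test and adds a Poisson mixed model, for which it names no offset for time.

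**The concern.** For a patient who completes 12 months on product, last dose and end of study nearly coincide and the wording is harmless. For a patient who stops at month 3 and keeps attending, the literal window closes at month 3, so a quarter-year count goes into a comparison of 12-month means. The arm with more product stops would look better on relapses for that reason alone. The within-arm comparison with the previous year, and the responder classification built on it, would set a shortened count against a full year.

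Because the window can be read in two ways, two programmers working from the same SAP could produce different primary results.

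**Working it through.** **The plan's own figure.** Inputs from Protocol 14.7 and SAP 7: means 2.6 and 2.0, SD 0.7, alpha 5%, power 80%. A two-sided two-sample t-test with 23 per arm (46 in total) has power 0.811; 22 per arm gives 0.793. Allowing for 20% dropout, 46/0.8 = 57.5, so 58 against the stated 60. The sample size reproduces and is not in dispute. It is built on full-year counts.

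**Assumptions.** The documents give no product-stop rates by arm and no stop times. Let p be the share of an arm that stops and f the mean fraction of the year lost by those who stop. All ITT patients are taken as analysed. The sentence in SAP 5.1 limiting the primary analysis to patients with relapses is a separate matter.

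**Means under the literal window.** The on-treatment mean is m × (1 − p × f), where m is the full-year mean. With no true effect (2.6 in both arms), the false difference is 2.6 × f × (p for NORFLO − p for placebo). At f = 0.5:

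- 30% versus 10%: 2.6 × 0.5 × 0.20 = 0.26, which is 43% of the planned 0.6. For f from 0.25 to 0.75 the range is 0.13 to 0.39.
- 25% versus 15%: 2.6 × 0.5 × 0.10 = 0.13.
- 20% versus 20%: 0.

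If the imbalance runs the other way, so does the bias: 10% versus 30% gives −0.26, against NORFLO.

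**Rejection rates with no true effect.** These were simulated with 30 per arm, stop times uniform over the year and independent of relapse, and a two-sided t-test at 5%.

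| Stopping, NORFLO / placebo | False difference | Rejection, count SD near 0.8 | Rejection, Poisson |
|---|---|---|---|
| 30% / 10% | 0.26 | about 17% | 8 to 10% |
| 25% / 15% | 0.13 | 7 to 9% | about 6% |
| 20% / 20% | 0 | about 5% | about 5% |

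**Power with a true difference of 0.6 and 20% stopping in each arm.** The on-treatment means are 2.0 × 0.9 = 1.80 and 2.6 × 0.9 = 2.34, a difference of 0.54 (0.57 to 0.51 for f from 0.25 to 0.75). Mixing full-year and part-year counts also widens the spread. In the placebo arm, take SD 0.7 and uniform stop times:

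- Variance among stoppers: 2.6/6 + (0.49 + 6.76)/3 − 1.3² = 1.16.
- Variance in the whole arm: 0.8 × 0.49 + 0.2 × 1.16 + 0.16 × 1.3² = 0.89, so the SD rises from 0.7 to about 0.95.

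Simulated power:

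| Count | SD near 0.8 | Poisson |
|---|---|---|
| On-treatment | about 60% | 26 to 28% |
| Full year, effect persists after stopping | about 84% | 32 to 33% |
| Full year, effect ends at stopping (difference also 0.54) | about 74% | about 28% |

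**The case against.** A reader might infer that the plan excludes relapses after the product is stopped, and so runs an on-treatment analysis under an ITT label. The documents do not support that. No sentence excludes them, the term is undefined, planned treatment and participation are equally long, and both endpoint definitions and the hierarchy refer to the study. A month-12 reading is open.

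It is not secured, however. Protocol 10.3 calls Visit 3 the end of study, not of treatment. Protocol 13.1 says expressly that adverse events are recorded during periods without product, and relapses have no such sentence.

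Four further objections carry weight:

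- **The affected group is limited.** Remaining visits are only encouraged. Systemic treatment for a relapse and emergency unblinding lead to study withdrawal. Non-compliance (Protocol 8.7) and violations (Protocol 12) may do so. The clearest remaining group is patients who stop for an adverse event and keep attending.
- **The inflation needs an imbalance.** It is small at 25% versus 15% and absent at equal stopping. The only related figure in the documents, the 20% dropout allowance, is not a rate of product stops.
- **The gain in power is partly conditional.** Some of it depends on the effect outlasting the product, and with Poisson counts there is little or none.
- **An on-treatment count can be a legitimate choice in an exploratory study.** If stopping is unrelated to relapse, as simulated here, a log-time offset would also remove the false difference. But no offset is named, and the t-test has none. Stopping that depends on relapse risk was not simulated.

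**Conclusion.** The point holds as an undefined counting window with no rule for relapses after product discontinuation. It does not hold as a stated exclusion. Followed literally, the wording puts part-year counts into a comparison of 12-month means.

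Under the assumed stopping patterns, the harm runs from no type I error inflation when stopping is equal to a false-positive rate of about 17% at 30% versus 10% with SD near 0.8. Equal stopping still costs power at that SD: about 60%, against 74 to 84% for a full-year count. These figures treat every stopper as remaining in follow-up, so they are an upper guide to what redefining the window can recover. The stated sample size is unaffected. This should be settled before unblinding, which SAP 4.3 places after database lock.

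**What to change.** In Protocol 5.1 and 14.3 and SAP 5.1 and 11.4.1, define the window as randomisation to month 12, or last study contact if earlier, whether or not the patient is still taking study product. Use the same window for the count, the intensity and the comparison with the previous year. State that relapses recorded in product stoppers who remain in follow-up are counted, and name log follow-up time as the offset in the Poisson model. Keep the on-treatment count as a sensitivity analysis.

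Fix month 12 by date, because Protocol 10.4 allows Visit 3 to be delayed. The lists for Visits 2 and 3 contain no relapse item, so any stoppers still in follow-up should be asked about relapses there. If follow-up is already complete, the rule can use only what was recorded.

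Protocol 10.4 withdraws patients given systemic treatment for a relapse from the study. Protocol 11.1 lists the need for systemic therapy as a reason to stop treatment, with remaining visits encouraged. These two sections must be reconciled on whether such patients stay in follow-up. The new window does not recover patients who have been withdrawn.

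The cost is about one sentence in each of the four sections, with no extra visits and no change in sample size. The downside is that the difference counted regardless of product use may be slightly smaller than the on-treatment one.

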7.1 Allowed Medications and Treatments

All topical drugs (any topical midriatic treatment and any traditional topical therapy for uveitis) will be admitted for the treatment of the signs and symptoms associated with HLA-B27-associated chronic relapsing uveitis.

In the case of relapse with LFM values are > 100 ph/ms despite treatment with topical therapy, or in any case the LFM values result to be > 100 ph/ms, then a systemic therapy is recommended and the subject has to be dropped-out from the study and treated according to the best medical judgement.

7.2 **Prohibited Medications and Treatments**

The following medications are prohibited during the study and the administration will be considered a protocol violation: supplements and nutraceuticals, systemic therapies for uveitis (anti-inflammatory, immunosuppressive, biologicals), hormonal contraceptives, long-term treatment with systemic anti-inflammatory, immunosuppressive or biological drugs for other diseases different from uveitis. Systemic therapies with anti-inflammatory, immunosuppressive drugs are allowed for reasons different from uveitis and in any case for periods not exceeding 15-30 days.

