## 11.5 Summary of Efficacy Analyses

| Endpoint   | Analysis  | Populations |
|--|---|-------------|
| The mean number and intensity of relapses
(primary endpoint)                | Student's t-test, ANOVA, generalized linear mixed model | ITT         |
| The reduction of mean number of relapses (primary endpoint)                    | Student's t-test, ANOVA                                 | ITT         |
| The difference of the level of cell damage and inflammation (primary endpoint) | ANCOVA  | ITT         |
| The changes in IOP (secondary endpoint)  | ANCOVA  | ITT         |
| The changes in OCT (secondary endpoint)  | ANCOVA  | ITT         |
| The changes in BCVA (secondary endpoint)                                       | ANCOVA  | ITT         |
| The presence of keratopathy (secondary endpoint)                               | Chi-square test   | JTT         |
| The presence of synechiae (secondary endpoint)                                 | Chi-square test   | ITT         |
| Information collected through the Quick questionnaire (secondary endpoint)     | Chi-square test   | ITT         |

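### The first-ranked relapse-number comparison uses raw counts with no time at risk, although some relapses end participation and so cut the count short

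*SAP*

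**What the plan says.** Protocol 14.3 and SAP 11.4.1 compare the mean relapse count per patient between arms: "The mean number of relapses per patient will be compared between the treatment groups using Student's t-test". ANOVA is added for covariates, and a Poisson generalized linear mixed model takes the relapse count as dependent variable. SAP 11.5 lists the methods for this endpoint as "Student's t-test, ANOVA, generalized linear mixed model". No efficacy section mentions an offset, a rate or follow-up time. Exposure appears only under safety (SAP 12.1). The counting window runs from baseline to end of treatment.

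Some relapses end participation. When flare exceeds 100 ph/ms, Protocol 7.1 says "a systemic therapy is recommended and the subject has to be dropped-out from the study". Protocol 10.4 says "If the subject is prescribed a systemic treatment for the relapse, he/she will be withdrawn from the study", but also "If only topical treatments are prescribed, the subject will be allowed to continue the study". Protocol 11.1 says of patients who stop study treatment that "they should be encouraged to complete all remaining scheduled visits and procedures".

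On the resulting gaps, SAP 9.1.4 says "No missing data will be replaced", and Protocol 11.2 says "Only subjects dropping out the study because they are beginning systemic therapy with antiinflammatory, immunosuppressive, biologic drugs will be replaced". The SAP does not say how a leaver or a replacement is counted.

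**The concern.** A raw count is comparable between patients only if each is observed for the same time. Here observation can stop because of the outcome. A patient withdrawn at month 1 after one severe relapse scores 1, while a patient with two mild relapses over twelve months scores 2. The efficacy population needs only one post-randomisation estimate (SAP 8.1), so the shortened count enters the test as if it were complete.

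Two things are at stake. If the arms lose patients at the same rate per relapse, the observed difference shrinks and power falls. If they do not, the arm whose relapses more often trigger withdrawal has fewer relapses counted, whatever its true rate. Lower severity is part of the primary objective (Protocol 3.1), so a product that makes relapses milder would be penalised on relapse number.

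**Working it through.** **1. The plan's own figure.** Inputs (Protocol 14.7, SAP 7): 2.6 vs 2.0 relapses, SD 0.7, alpha 5% (taken as two-sided), power 80%. The t-test calculation gives 22.4, so 23 per arm and 46 in total, with 81% power. This reproduces the stated 46. Dropout: 46/0.8 = 57.5, so 58; the plan says 60. At 30 per arm with complete counts, power is 90%. The sample-size arithmetic is not at fault.

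**2. Effect of truncation.** Let each relapse end participation with probability p. For Poisson relapses at yearly rate λ:

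- expected count = (1 − e^(−λp))/p
- share withdrawn = 1 − e^(−λp)

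| p (both arms) | Placebo count | Product count | Difference | Withdrawn, placebo / product |
|---|---|---|---|---|
| 0 | 2.60 | 2.00 | 0.60 | 0% / 0% |
| 0.1 | 2.29 | 1.81 | 0.48 | 23% / 18% |
| 0.2 | 2.03 | 1.65 | 0.38 | 41% / 33% |

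With counts simulated at the plan's SD of 0.7 (rounded normal, latent SD √(0.49 − 1/12) = 0.638), the differences are 0.50 and 0.41.

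**3. What p might be.** The documents do not give it.

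- If the whole 20% dropout allowance were relapse-driven on placebo, 1 − e^(−2.6p) = 0.20, so p = 0.2231/2.6 = 0.086. The difference is then 2.33 − 1.84 = 0.49.
- Protocol 2 cites 44 acute HLA-B27 episodes with initial flare 160 ± 22 ph/ms, range 11–787. The 22 cannot be an SD: (787 − 160)/22 = 28.5 SDs, and the largest deviation possible in 44 values is 43/√44 = 6.5 SDs. Read as a standard error, the SD is 22 × √44 = 146. Then at least 8 of 44 (18%) exceed 100, and about 58% do if flare is log-normal. Values of p above 0.09 are therefore possible.

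**4. Power with equal p.** Simulation: 30 per arm, SD 0.7, relapses at uniform times over the year, at least 10,000 trials per setting, no covariates. The replacement columns assume one replacement in the same arm.

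| p | t-test, no replacement | t-test, leaver and replacement both analysed | t-test, leaver omitted | Rate model with offset, no replacement |
|---|---|---|---|---|
| 0 | 90% | – | – | 90% |
| 0.1 | 70–72% | 79% | 86% | 81% |
| 0.2 | 51–52% | 65% | 73% | 70% |

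The t-test's size stays at about 5% when the true rates and p are equal.

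**5. Unequal p, equal true rates (2.6 in both arms).** Nominal error in each direction is 2.5%.

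| p placebo / product | t-test falsely favours | Poisson counts | SD 0.7 |
|---|---|---|---|
| 0.4 / 0.2 | placebo | 26% | about 40% |
| 0.1 / 0.2 | product | 11% | 17% |

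With the planned 2.6 vs 2.0 and p of 0.4 vs 0.2, the expected difference is 1.62 − 1.65 = −0.03 (Poisson): the true benefit disappears.

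**6. The rate model under the same stress.** With equal true rates and lower p on the product, the offset model falsely favours the product in 2.5–3% of trials under Poisson counts, but in about 6–14% at SD 0.7.

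These figures include patients with zero relapses. SAP 5.1 limits the primary endpoints to patients who relapsed; that is a separate defect.

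**The case against.** A reader might infer that the t-test must lose most of its power, or that the design favours the product. The documents support neither.

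- **Replacement.** Protocol 11.2 and 14.7 replace exactly the patients who leave for systemic therapy, and this recovers much of the power. The objection stands in part: Protocol 8.1 and SAP 4.2 put enrolment at 60, so it is unclear whether replacements come on top. The stated plan is also 80% power at 46 evaluable patients, not 90%.
- **Size of p.** At p = 0.2 the placebo arm would lose 41% of its patients, against 20% planned from all causes. Exclusion criterion 3 also removes patients expected to need systemic drugs. This argues against treating high p as the base case, but it does not make p zero.
- **Direction.** With equal p the error is conservative and the sign is kept. A false claim for the product needs its relapses to trigger withdrawal more often, and the intensity comparison, which shares first rank, might show that. It would not correct the count.
- **Dropout allowance.** It adds patients. It does not correct counts that relapse itself cut short.
- **Remaining visits.** The encouragement in Protocol 11.1 sits badly with withdrawal from the study, and the counting window closes at end of treatment.
- **The remedy.** A reader might take the offset for a clean repair. Step 6 shows it is not when p differs between arms and counts vary less than Poisson.

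**Conclusion.** The concern holds. As written, the first-ranked relapse-number comparison treats counts of unequal length as equal, and the inequality is caused by the outcome. With equal p the cost is a smaller difference and lower power, moderate at p near 0.1 and larger at 0.2, with replacement softening both. With unequal p the comparison is biased in either direction, well beyond the nominal error. The sizes rest on an assumed p, uniform relapse timing, the plan's SD of 0.7 or Poisson counts, and 30 per arm. That the plan names no time at risk rests on no assumption. The documents do not show that p is large or that it differs between arms, so they do not support saying that the result will be wrong, only that the planned analysis cannot guard against it.

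**What to change.** Before unblinding, amend the SAP as follows.

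- Compare relapse number as a rate, using the Poisson model already planned with a stated log link, log(time at risk) as offset, and robust standard errors with a stated small-sample correction. Without robust errors, the Poisson offset model has only 16–17% power at SD 0.7. Adjust for site (SAP 9.2) and prior-year relapse count (recorded at Visit 1).
- Include all randomised and treated patients: those with no relapse, those withdrawn, those replaced and their replacements, each with their own count and time.
- Define time at risk to match the window from baseline to end of treatment, including a delayed Visit 3 (Protocol 10.4).
- Keep the t-test as supportive, and report relapse-triggered withdrawals by arm.
- State that the offset leaves bias if p differs between arms. Read the result with a log-rank test of time to first relapse, which withdrawal at a relapse cannot distort but which has only 16–20% power, and with analyses that impute the lost months at the own-arm rate and at the placebo rate.
- Reconcile the withdrawal and follow-up statements in Protocol 7.1, 10.4 and 11.1. Because the SAP describes enrolment and treatment in the past tense, document which rule was actually applied.

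The cost is a SAP amendment and modest programming, with no new patients or visits. It must be confirmed that relapse and withdrawal dates were captured, since the case report form is not among the documents.
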